Cancer Treatment Variables. Clinical variables including date of diagnosis, malignancy type (smoking related vs. non-smoking related, cancer stage), and treatment details (i.e. types and dates of surgery, chemotherapy, and/or radiation received), along with disease status and survival, will be captured in Medidata Rave via the parent protocol and will be available for analysis of the ancillary. Provider-assessed adverse events will also be captured via the parent protocol in Medidata Rave, using case report forms commonly used across the NCTN and using standard data elements.

Assessments

All items in Survey of Tobacco Use will be administered using the EASEE-PRO system. The advantage of our virtual electronic data capture system is that our proposed assessments will not be limited to, or dependent upon, patient trial visits. Confidential and potentially stigmatizing information can be provided without requiring direct contact with the care team.

Timing of Assessments

Given the critical questions that remain¹³ about the timing of conducting tobacco use assessments, we have carefully chosen to collect tobacco assessment data at trial enrollment, 3 and 6 month follow-up. For tobacco treatment trials, 6 month follow-up is the recommended primary outcome time point. By 6 month follow-up, most cancer treatment-related quitting activity⁶², cancer treatment initiation of therapy, and FDA-approved smoking cessation medication regimens will be completed. Adverse events during treatment will have been observed.

Statistical Considerations and Analysis Plans

The analysis plans described below are planned for a combined analysis of the data from the 8 selected ECOG-ACRIN trials. Consistency in the effects over the studies would be examined in this analysis.

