1. CHANGES IN SMOKING STATUS AND EXPOSURE. At baseline, combustible tobacco use (1a) will be characterized by smoking status (never smoker, former smoker, and current smoker based on Baseline STU Qs 1 and 5), other forms of tobacco use (1b) will be a composite variable determined by non-cigarette items (based on Baseline STU Q7 and Q14), and environmental tobacco smoke (ETS) level (1c) will be determined by current household and work exposure (Baseline STU Qs 15-16). At follow-up, combustible tobacco use (1a) will be examined by smoking status (Follow-up STU Qs 1 and 2), other forms of tobacco use (1b) will be determined by Follow-up STU Q10, and ETS level (1c) will be determined by 30 day household and work exposure (Follow-up STU Qs 11-12). We will examine tobacco use at baseline, 3 and 6 month follow-up, and change in status (abstinence in combustible tobacco, abstinence of other forms of tobacco use, and change

Rev. Add4

in exposure to smoke-free home and work) using summary statistics (frequency and proportion). We will explore the effects of sociodemographic and cancer treatment factors on smoking status using logistic regression (comparing smokers and non-smokers). We will also evaluate factors associated with changes in smoking status.

2. **TREATMENT TOXICITY.** The selected trials capture information about adverse events during treatment using NCI's Common Terminology Criteria for Adverse Events. Toxicities are measured at each treatment visit and graded according to severity, with grade 1 corresponding to mild toxicity and grade 5 signifying a lethal adverse event. We will determine each patient's worst degree toxicity across all event types and treatment visits and will compare the distribution of worst degree grades between smokers and non-smokers and between patients with environmental tobacco exposure and those without exposure using exact tests. We will also examine the distribution of worst degree grades between users with different form of tobacco use. In addition, we will explore the effects of tobacco use on dose modifications (yes vs. no) using logistic regression, with each patient's dose modification status determined across all treatment visits.

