3. **SYMPTOM BURDEN.** Tobacco variables will be conceptualized as described in the section of CHANGES IN SMOKING STATUS AND EXPOSURE. Tobacco use status (as measured at baseline, 3 and 6 month follow-up) will be compared to physical and psychological symptom burden (as measured at each corresponding time points). At 3 and 6 month follow-up, we will also examine the association between tobacco use changes and changes in symptom burden. We will explore the effects of sociodemographic and cancer treatment factors on symptom burden using repeated measures mixed effects models. As an example of statistical power, we consider the PROMIS SF-4 depression measure. We assume that 1500 patients will be enrolled across the 8 parent studies over 13 months, and that 20% are smokers. We assume that 85% of patients will have assessments at 6 months. Given groups of these sizes (26 quitters and 230 still-smokers) and standard deviation of 4.08 for the PROMIS SF-4 depression scale, there will be 83% power to detect a difference in change scores of 2.5 between groups using a two-sample t-test with Type I error of 5%. The minimally important difference for this instrument is 2.2.⁷⁹
4. **CESSATION PATTERNS AND TREATMENT.** At baseline we will explore pre-treatment combustible tobacco use patterns (STU Q6a and Q6b), quitting behaviors (STU Q13), behavioral program utilization (STU Q11) and oncology provider support (5As, STU Q12), and smoking cessation medication use (STU Q10). At follow-up we will explore post-treatment combustible tobacco use patterns (STU Q3a-Q3e), quitting behaviors (STU Q9), behavioral program utilization (STU, Q7) and oncology provider support (5As, STU Q8), and smoking cessation medication use (STU Q6). We will explore the effects of sociodemographic and cancer treatment factors on these variables. We will examine associations of quitting behaviors and behavioral and medication utilization with tobacco use status (as outlined in the section of CHANGES IN SMOKING STATUS AND EXPOSURE) at baseline and on respective 3 and 6 month tobacco outcomes. These analyses will be descriptive in nature. Summary statistics (frequency, proportions, and 95% confidence intervals) will be used.

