5. **TRIAL OUTCOMES.** We will compare treatment duration between smokers and non-smokers and between patients with environmental tobacco exposure and those without exposure. Cumulative incidence/competing risk methods will be used to estimate time to treatment discontinuation for adverse events, disease progression, completion per protocol, or other causes. Gray's test will be used to test for differences in the cumulative incidence distributions.⁷⁸ Differences in the distribution of reasons for discontinuation of treatment will be examined using exact tests. Relative dose intensity is defined as the ratio of actually delivered dose intensity to the planned dose intensity. The effects of tobacco use and

exposure on relative dose intensity ($\geq 90\%$ vs. $< 90\%$) will be explored using logistic regression. Differences in the primary endpoint and important secondary endpoints will be examined using log rank test and exact test (as appropriate).

Data collected in the tobacco use project will support a range of analyses. Precise estimates of power will depend on the prevalence of smoking at baseline among study participants, the proportion whose smoking status changes, and the duration and adequacy of follow-up.

References

1. YI, Yang P, Parkinson J, Zhao X, Wampfler JA, Ebbert JO, Sloan JA. The relationship between cigarette smoking and quality of life after lung cancer diagnosis. *Chest*. 2004; 126(6):1733-1741. doi: 10.1378/chest.126.6.1733.
2. Gritz E. Rationale for Treating Tobacco Dependence in the Cancer Setting. Conference presentation at: Treating Tobacco Dependence at the National Cancer Institute's Cancer Centers. December 2009.

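### The pooled 8-trial tobacco comparisons name no stratification by parent trial, so they can show a tobacco effect that exists in no trial, or hide a real one, if smoking and outcome rates vary together across trials

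*Combined protocol and SAP*

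**What the plan says.** The opening of the statistical section of Appendix VIII says that the analyses are "planned for a combined analysis of the data from the 8 selected ECOG-ACRIN trials". It adds one sentence on differences between trials: "Consistency in the effects over the studies would be examined in this analysis". No method is named for that check.

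The comparisons at issue are these:

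- **Item 2 (treatment toxicity).** The plan will "compare the distribution of worst degree grades between smokers and non-smokers" and likewise "between patients with environmental tobacco exposure and those without exposure using exact tests". Dose modification is handled separately: the plan will "explore the effects of tobacco use on dose modifications (yes vs. no) using logistic regression", with no covariates listed.
- **Item 3 (symptom burden).** The plan explores "effects of sociodemographic and cancer treatment factors on symptom burden using repeated measures mixed effects models". Parent trial is not named as a factor.
- **Item 5 (trial outcomes).** For treatment duration, "Gray's test will be used to test for differences in the cumulative incidence distributions". Reasons for discontinuation are compared by exact tests, and relative dose intensity by logistic regression. For the trials' own endpoints: "Differences in the primary endpoint and important secondary endpoints will be examined using log rank test and exact test (as appropriate".

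No stratum is named in any of these items. By contrast, section 9.3 says explicitly that the primary PFS log rank test is stratified on the randomization factors.

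Section 1.8 says that the pooled trials cover cancers with and without a tobacco link and a range of treatments. The note under section 2.5 says that these objectives are ancillary and that the tobacco data stay out of this trial's clinical study report.

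**The concern.** Parent trial can influence both sides of the comparison. Smoking prevalence plausibly differs between a trial in a tobacco-related cancer and one in another cancer. Severe toxicity, time on treatment and survival differ by disease and regimen. If the two move together across trials, smokers are over-represented in the trials with high (or low) event rates, and a pooled two-group test reads that difference in case mix as an effect of smoking. If they move in opposite directions, the pooled test can cancel a true effect.

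What is at stake is the answer to objectives 2.5.1 (toxicity) and 2.5.4 (treatment duration, dose intensity and therapeutic benefit). The consistency check would produce study-level effects, but the p-value from the combined test would still mix within-trial and between-trial differences.

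**Working it through.** **The plan's own figure.** The only power statement in Appendix VIII is in item 3: 26 quitters against 230 continuing smokers, SD 4.08, difference 2.5, type I error 5%, power 83%. The noncentrality is 2.5 / (4.08 × √(1/26 + 1/230)) = 2.96. The two-sided noncentral t with 254 df gives 83.9%, so the figure reproduces. The group sizes also agree: 1,500 × 0.20 × 0.85 = 255, against 26 + 230 = 256. This figure does not bear on the smoker versus non-smoker tests, for which no operating characteristics are given.

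**Inputs for the check.** From item 3: 1,500 patients, 20% smokers. Assumed, because the documents do not give them: per-trial smoking prevalence and per-trial severe toxicity rate (worst grade reduced to severe or not). In every scenario smoking has no effect within any trial. Section 1.8 puts smoking at diagnosis at about 10% to 30% of cancer patients, and that range bounds the assumed prevalences.

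**One case by hand.** Half the patients come from trials with 30% smokers and 60% severe toxicity, half from trials with 10% and 30%.

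- Smokers: 750 × 0.30 + 750 × 0.10 = 225 + 75 = 300. Severe: (225 × 0.60 + 75 × 0.30) / 300 = 157.5 / 300 = 52.5%.
- Non-smokers: 525 + 675 = 1,200. Severe: (525 × 0.60 + 675 × 0.30) / 1,200 = 517.5 / 1,200 = 43.1%.
- Pooled rate 675 / 1,500 = 45%. SE = √(0.45 × 0.55 × (1/300 + 1/1,200)) = 0.0321.
- z = (0.525 − 0.431) / 0.0321 = 2.92. The chance of rejection at two-sided 5% is about Φ(2.92 − 1.96) = 83%. The crude odds ratio is 1.46, although it is 1 in every trial.

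**Simulation.** Pooled Fisher exact test against the Cochran-Mantel-Haenszel (CMH) test stratified by trial or trial group, both at two-sided 5%, with 3,000 to 4,000 datasets per scenario.

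| Smoking in the two sets of trials | Severe toxicity in the same sets | Link | Crude OR | Pooled test rejects |
|---|---|---|---|---|
| 20% / 20% | 40% / 60% | none | 1.00 | 4.1% |
| 10% / 30% | 50% / 50% | none | 1.00 | 4.7% |
| 10% / 30% | 40% and 60% in each set | none | 1.00 | 4-5% |
| 15% / 25% | 45% / 55% | modest | 1.06 | 7-8% |
| 15% / 25% | 40% / 55% | modest | 1.10 | 11-12% |
| 15% / 25% | 30% / 60% | moderate | 1.21 | 30-31% |
| 10% / 30% | 40% / 55% | moderate | 1.21 | 30-32% |
| 10% / 30% | 40% / 60% | moderate | 1.28 | 47-48% |
| 10% / 30% | 30% / 60% | strong | 1.46 | 82-83% |
| 10% / 30% | 30% / 70% | strong | 1.66 | 97% |

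The stratified test rejects in 4.5% to 6.0% of datasets in every row.

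**Hiding an effect.** Reversing the 10%/30% and 40%/60% case gives a crude odds ratio of 0.78. A true within-trial odds ratio of about 1 / 0.78 = 1.28 would then be roughly cancelled in the pooled table.

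**The case against.** **The plan is silent, not wrong.** Appendix VIII nowhere says that the tests are unstratified, and an analyst could add strata. That is fair as a matter of wording. But section 9.3 writes stratification where it is intended, and Appendix VIII names ordinary two-group tests without it. Run as written, those are the pooled versions.

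**The bias is conditional.** A reader might infer that differences between trials will be reported as smoking effects. The documents do not support that. Bias needs smoking and outcome rates to vary together, no per-trial rates are given, and the unlinked rows of the table show no inflation. This objection stands in full and limits the claim to what can happen. The simulation also reduces worst grade to a binary outcome and uses the same two-level pattern across trials, so it illustrates the mechanism and does not predict the result.

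**The consistency check is a safeguard.** It would show study-level effects, and in the scenarios above it could reveal that no trial has one. That has value. It has no stated method, however, and leaves the combined p-value and estimate uncorrected.

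**Arm is not a general confounder.** Correct. Within a randomized parent trial, such as Arms A to C here (1:1:1, section 9.7), baseline smoking is balanced over arms in expectation. Only non-randomized cohorts such as Arm T raise the issue.

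**Some analyses already allow adjustment.** Also correct. Dose modification and relative dose intensity use logistic regression, item 3 mentions treatment factors, and item 4 is descriptive. These need a named covariate, not a different test.

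**Conclusion.** The point holds as a conditional weakness. In a combined analysis of 8 unlike trials, the toxicity, discontinuation and endpoint comparisons name no stratification by parent trial, and the consistency sentence does not replace it. The false-positive rate at nominal 5% runs from about 4-5% (rates not linked) through 7-12% (modest link) to over 80% (strong link), against about 5% when stratified by trial. These figures rest on the plan's 1,500 patients and 20% smokers, and on assumed per-trial rates; which row applies cannot be known from the documents.

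A reader might go further and conclude that this trial's findings are at risk. They are not: the objectives are exploratory, belong to a separate ancillary project, and are excluded from this trial's clinical study report. This is a nearly free improvement to the analysis of objectives 2.5.1 and 2.5.4.

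**What to change.** In Appendix VIII:

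- **Items 2 and 5:** make parent trial the stratum for every smoker versus non-smoker and exposed versus unexposed comparison. Use CMH or stratified exact tests for worst grade and reasons for discontinuation, a stratified Gray's test for time to discontinuation, and a stratified log rank test for time-to-event endpoints. Give non-randomized cohorts such as Arm T their own stratum. Randomized arms need not be strata, which keeps the strata from becoming sparse.
- **Regression models:** include parent trial as a factor in the logistic models for dose modification and relative dose intensity, and in the item 3 mixed models.
- **Consistency:** name the method, for example study-level estimates with a test of the tobacco-by-trial interaction.

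The cost is wording. No new data are needed, because trial membership is known and Appendix VIII already makes malignancy type and treatment details available. Little precision is lost. Information on the smoking contrast is proportional to the sum of n × p × (1 − p), where p is the proportion of smokers. With 10% and 30% smokers in the two halves this is 750 × 0.09 + 750 × 0.21 = 225, against 1,500 × 0.16 = 240 pooled. Because the analysis spans 8 trials, the same wording has to be agreed for the ancillary project as a whole, not only in this protocol's appendix.
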